6.4 STUDY INTERVENTION COMPLIANCE

Blank Study diary will be dispensed to the Subject from Baseline Visit (V2). The Study Nurse will receive the blank diary from the Subject and record the daily compliance of the following during the Treatment Phase (V2-V14) as applicable:

- a. Off-loading
- b. Daily applications of the treatment (to confirm the dose application schedule),
- c. Missed applications,
- d. Excess dose drawing
- e. Completion of dressing of the Target Ulcer
- f. Any unusual happening

The Study Nurse will not disclose these entries to the Subject and retain the Study diary with her before submitting it to the unblinded Investigator. Collection and review of Study diary will

continue from V3 till V12 or EOT. The un-blinded Investigator will transcribe the information from the Study diary into the CRF. During the Treatment Phase, unblinded Investigator should record the weight of single application of treatment prescribed during every Treatment visit of the Subject and this basis will be used to check weekly compliance of the dose. The dose to be applied will be informed to the Study Nurse by the unblinded Investigator after every weekly Treatment visit. During Follow-Up Phase (V15-V18), Subject diary will be filled and handled by the Subject since there will be no treatment provided during the Follow-up. The Subject will hand over the completed Study Diary to the un-blinded Investigator during Follow-up visits.

The Subjects with treatment compliance of less than 80% or more than 120% of the IP, during the week, will be considered treatment non-compliant for that week. If such non-compliance is observed for more than three weeks, and if the blinded Investigator opines that it may affect the outcome of the Study, then the Subject shall be considered non-compliant for the Study and shall be discontinued from the Study.

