6.2 PREPARATION/HANDLING/STORAGE/ACCOUNTABILITY

6.2.1 ACQUISITION AND ACCOUNTABILITY

The Sponsor/Contract Research Organization (CRO) will provide IP (Galnobax® as well as Vehicle gel) to the site. The accountability of IP will be maintained as follows:

- The Investigator/co-Investigators or designee would acknowledge receipt of Study IP supplies for each shipment received
- The unblinded Investigator responsible for dispensing the IP to the Study Nurse must maintain a drug accountability log. The IP accountability log records the receipt, dispensing and return of the IP
- At any time the sum of quantity of used and unused IP should match with the quantity of medication supplied. Account must be given of any discrepancies
- The Study monitor and Sponsor should be notified immediately of details of any IP, which is inadvertently damaged or lost
- The used or unused IP tubes will be returned by the Study Nurse to the site. Tubes will be replenished as required with identical kit number
- The quantity of IP utilized for the treatment will be monitored by checking the weight of the tube at the time of issuing it for the treatment and at the time of collecting the used tube
- If all tubes from the kit are consumed, a new kit with identical treatment will be issued

Handling of Investigational Product:

Both used and unused IP tubes would be sent back to Sponsor/their representative for destruction as per standard procedure. Reconciliation between the amount of IP supplied, used and returned to the Sponsor must be performed by the Sites and the CRO. If any discrepancies are found in the reconciliation of IP, it will be resolved. This reconciliation will be logged by each site on the IP reconciliation form, signed and dated.

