6.3 MEASURES TO MINIMIZE BIAS: RANDOMIZATION AND BLINDING

This is a double-blind study wherein the Investigator, the Sponsor, the Subject, the CRO and the Study Nurse Coordinator will be kept blinded to the randomization throughout the Study. There will be one unblinded Investigator per site who will administer the treatment during each treatment visit of the Subject as well as dispense the IP to the Study Nurse and the SoC material to the Subject. The Study Nurse who will administer treatment to the Subject (twice daily during Treatment Phase) will be unblinded. However, the unblinded Investigator and Study Nurse will still remain blinded to whether the Study drug applied is Galnobax® or Vehicle gel. The blinding of the Subject will be ensured by the Study Nurse by using shield while treating the Target Ulcer.

In case the Subject is staying far from the site (i.e. 40 km or more from the site) and/or Nurse is unable to visit every week to the site for treatment compliance check, following procedure will be followed for IP transport and compliance check: IP will be issued to the study Nurse at the time of the randomization visit along with study diary in an aluminum box having a lock. One key of this lock will be with the study Nurse and other with the unblinded CRC at the site. At the time of weekly site visit of the Subject, study Nurse will keep used IP tubes and Study diary in this box which will be locked and sent to the site with the Subject. Site unblinded CRC will take aluminum box from the subject and will check IP compliance as well as study diary. The IP will be reissued to the nurse after weighing the tubes and new study diary will also be issued (through which new dose of the subject will be conveyed to the Nurse). These materials will be kept in the aluminum box which will be locked and given to the Subject for handing over it to the study Nurse. This process will continue during all treatment visits.

While the IP compliance will be verified by the unblinded Investigator, the Target Ulcer Closure will be decided and confirmed by the blinded Investigator, thus mitigating any bias.

Unblinding will be done only if necessary for the welfare of the Subject or in the case of emergency suspected to be IP related. If such emergency is clearly not IP-related in the opinion of the Investigator, the Subject management can be done without the need of unblinding. Standard norms and procedures for unblinding will be followed.

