7.2 PARTICIPANT DISCONTINUATION/WITHDRAWAL FROM THE STUDY

Participants are free to withdraw from participation in the Study at any time. If the withdrawal happens during the Treatment /Follow up Phase, the last visit prior to withdrawal will be treated as EOT/EOS visit and corresponding CRF will be completed by the Investigator.

Subjects who sign the informed consent form (ICF) and are randomized but do not receive the study intervention will not be replaced and will not be part of ITT Population.

Subjects who sign the ICF, and are randomized and receive the study intervention, and subsequently withdraw, or are withdrawn or discontinued from the study, will not be replaced and yet be part of ITT Population.

Subjects must be discontinued from the Study after randomization if any of the following events occur (Stopping or Discontinuation Rules for Individual Subjects):

1. A Subject withdraws consent
2. Investigator recommends that the Subject should discontinue the participation in the Study
3. Subject misses two consecutive Weekly Visits during Treatment Phase
4. If the Target Ulcer and the adjoining wound merge together and if the Investigator opines that following the Target Ulcer is difficult. A detailed note by the Investigator will be recorded in the e-CRF outlining reasons for such merger in line with the preceding measurement of Target Ulcer
5. If Subject requires hospitalization for more than two consecutive weeks during the Study
6. The Subjects with treatment compliance of less than 80% or more than 120% during the week, will be considered treatment non-compliant for that week. If such non-compliance is observed for more than three weeks, and if the blinded Investigator opines that it may affect the outcome of the Study, then the Subject shall be considered non-compliant for the Study and shall be discontinued from the Study
7. If the blinding of a Subject is compromised
8. Any form of major protocol violation
9. The Target Ulcer increases in size (more than 30%) for two consecutive weeks or requires deep, surgical debridement for more than two occasions during the Treatment Phase to address Target Ulcer deterioration
10. The Target Ulcer becomes infected requiring topical antimicrobial treatment
11. If Subject develops osteomyelitis or cellulitis during the Study on the foot having the Target Ulcer
12. If female Subject becomes pregnant, during the study
13. If Subject misses 6 consecutive dressings

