10.1.8 PROTOCOL DEVIATIONS

During the conduct of the Study, if any deviation(s) is noticed from the norm mentioned in the Protocol, this will be documented as protocol deviation(s).

The severity of the protocol deviation will be graded as minor if the deviation is not altering the integrity of the Study plan or its safety and efficacy outcome. The deviation is said to be major or is designated as violation, if it is altering the integrity of the Study plan or its safety and efficacy outcome in the opinion of the Investigator.

Examples of the major deviations or violations of the Protocol shall include:

- Recruitment of a Subject in conflict with the inclusion and exclusion criteria
- If Subject misses two consecutive Treatment visits or maximum of four Treatment visits
- If Subject misses 6 consecutive wound dressings, anytime during the Treatment Phase
- If Subject misses both of the Closure Verification Visit as well as Closure Confirmation visit
- Use of a non-permitted concurrent treatment
- Failure to obtain informed consent prior to initiation of Study related procedures

Examples of minor deviations of the Protocol shall include:

- Visits that occurred outside the time frame permitted in the protocol
- Subjects have not met with Study drug compliance (80% - 120%) for a week during Treatment Phase

- Laboratory tests not performed as per timelines specified in the protocol

Protocol Waivers

There are no protocol waivers proposed for this Study.

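### Protocol 6.4 and 7.2 item 6 ask the blinded closure assessor to rule on non-compliance, which can signal a gel arm and decide FAS membership

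*Combined protocol and SAP*

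**What the plan says.** Section 6.3 sets out the safeguard: "While the IP compliance will be verified by the unblinded Investigator, the Target Ulcer Closure will be decided and confirmed by the blinded Investigator".

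Section 6.4 defines a non-compliant week as "treatment compliance of less than 80% or more than 120% of the IP", checked against the weight of the application prescribed at the weekly visit. After more than three such weeks the subject is removed, but only "if the blinded Investigator opines that it may affect the outcome of the Study". Section 7.2 item 6 puts the same rule in the list of mandatory discontinuations. There the limit reads "treatment compliance of less than 80% or more than 120% during the week" and does not name the IP.

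Three other places bear on what the limit measures.
- Section 6.2.1 says the Sponsor or CRO will "provide IP (Galnobax® as well as Vehicle gel) to the site". Use is "monitored by checking the weight of the tube at the time of issuing it", and again when the used tube is collected.
- Section 10.1.8 lists failure to meet "Study drug compliance (80% - 120%) for a week during Treatment Phase" as a minor deviation. Section 6.3 says unblinded staff remain blind to "whether the Study drug applied is Galnobax® or Vehicle gel".
- Section 6.1.2 gives the SoC arm saline cleaning and dressing, with no gel step.

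Section 9.3 admits to the FAS only randomized subjects with at least six weekly closure assessments, or with closure before six weeks. Section 9.4.1 analyses efficacy in the FAS and PP sets only, comparing Galnobax plus SoC with SoC alone.

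**The concern.** The person who judges the primary endpoint is brought into a compliance question that section 6.3 assigns to someone else. If the question can arise only where gel is dispensed, asking it tells the assessor that the subject is probably not in the SoC arm, and SoC is the comparator. Nothing in the plan says how the case is to be presented without revealing this, and nothing requires a matching query for SoC subjects.

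Two things follow. A flagged subject who is retained is later judged for closure by someone holding that signal. And the decision to remove is discretionary, made by someone who sees the ulcer every week, and can take the subject out of the primary analysis.

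**Working it through.** **Inputs.** Allocation is 3:3:1, Galnobax : SoC : Vehicle (section 4.1). The trigger is more than three failing weeks (6.4, 7.2 item 6). The FAS needs six weekly assessments (9.3). The target is 120 evaluable subjects per efficacy arm, with assumed closure of 39% on SoC and 60% on Galnobax (9.2).

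**The plan's own figure.** The pooled two-proportion formula, two-sided 0.05 and 90% power, is n = [1.960·√(2·0.495·0.505) + 1.282·√(0.39·0.61 + 0.60·0.40)]² / 0.21², which gives 118 per arm. At 120 per arm the power is 0.907, and 240/0.8 = 300. The sample size reproduces to within rounding and does not depend on this point.

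**What a query tells the assessor.** Let r be the rate at which SoC subjects are flagged relative to gel subjects. Assume that Galnobax and Vehicle subjects are flagged equally often. By Bayes' rule:

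P(SoC | query) = 3r/(3r + 4), and P(Galnobax | query) = 3/(3r + 4).

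With no query, each is 3/7 = 42.9%.

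| r | P(SoC) | P(Galnobax) |
|---|---|---|
| 0 (gel only, as 6.4 is worded) | 0% | 3/4 = 75.0% |
| 0.25 | 0.75/4.75 = 15.8% | 3/4.75 = 63.2% |
| 0.5 | 1.5/5.5 = 27.3% | 3/5.5 = 54.5% |
| 1 | 3/7 = 42.9% | 3/7 = 42.9% |

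The documents give no value for r; rows other than the first are assumptions. Only at r = 1 does the query carry no information.

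**Unit of effect on the closure call.** At 120 per arm, one changed call moves an arm's rate by 1/120 = 0.83 percentage points. This is a unit, not an estimate, because no flag rate is given.

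**Timing and the FAS.** More than three weeks means at least four, so the earliest decision is at week 4 (V6), after four post-baseline visits. A decision at week 5 comes after five. Both are below six. If a site counts the Baseline visit, the totals are five and six, and only week 4 falls short. From week 6 a subject who attended every visit already qualifies.

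**Unit of effect on the FAS.** At the assumed 60%, 72 of 120 Galnobax subjects close. One more subject with an open ulcer, kept and counted as not closed, gives 72/121 = 59.5%; leaving that subject out restores 60.0%. Each such exclusion is worth about 0.5 points.

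**The case against.** The strongest reply is that the gel-only reading is not secure. The rule concerns treatment compliance, and the protocol treats SoC as a treatment: section 4.1 has the nurse give twice-daily treatment in all arms, Table 2 lists SoC as twice daily, and the schedule's weekly compliance check names no arm. The protocol also uses IP loosely. Section 9.4.4.1 dates treatment-emergent events from the first IP dose, yet safety is analysed in all three groups. Item 6 does not name the IP at all. This stands: the fall from 43% to 0% is conditional on the 6.4 wording. Against it, the tube weights, the label in 10.1.8 and an upper limit of 120% all fit gel better than dressings, and missed dressings have their own rule in 7.2 item 13.

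Second, the route to a biased closure call is narrow. A removed subject has no later assessment, so the subject must fail four weeks, be queried, be retained, and then present a doubtful closure. A trained nurse applies the treatment. Closure means full re-epithelialization confirmed at two further visits. Section 7.2 item 7 also discontinues a subject whose blinding is compromised, although that would cost another subject. This limits the size of the problem; it gives no reason for asking the assessor.

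Third, whether non-compliance affects the outcome is a judgement, and a blinded person may seem the right one to make it. That holds while the rule is discretionary. A fixed rule needs no judgement.

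Fourth, early loss from the FAS follows from any early removal under 7.2. That is correct. What is particular here is that the endpoint assessor's opinion decides it.

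**Conclusion.** Sections 6.4 and 7.2 item 6 break the separation of roles that section 6.3 relies on, and a small change would restore it. The signal ranges from complete (gel or not) at r = 0 to none at r = 1, and the wording favours the lower end. The number of subjects affected is unknown and probably small.

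A reader might infer that the assessor is thereby unblinded to the allocation. The documents do not support that: the query never separates Galnobax from Vehicle, item 6 leaves room for SoC subjects to be flagged, and the plan does not say what else the assessor is shown. Nor do they support a claim that the primary comparison is biased by any stated amount, since neither a flag rate nor a count of retained subjects can be derived. The FAS consequence is confined to removals around weeks 4 and 5 with the ulcer still open. This is a worthwhile improvement to the plan, not a defect that invalidates it.

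**What to change.** Delete the blinded Investigator's opinion from 6.4 and 7.2 item 6, and take this rule out of the removal list. Instead:

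- The unblinded Investigator, who stays blind to Galnobax versus Vehicle, applies the existing limit with no discretion: outside 80–120% of the dose and frequency prescribed for that week, in more than three weeks. Scoring against the prescription means that frequency changes under 4.3 and deferrals under 6.5 do not count as failures.
- A hit is recorded as a protocol deviation that bears on the PP set. Its grade should be fixed in advance, because 10.1.8 leaves grading to the Investigator's opinion. If it is graded major, exempt it from 7.2 item 8, which would otherwise force the removal that this change avoids.
- No flag goes to the closure assessor. The scheduled blinded weekly and follow-up assessments continue, and the subject stays in the primary analysis.
- State whether the limit covers SoC applications, so that 6.4, 7.2 and 10.1.8 agree.

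An automatic gel stop is not needed. It would withdraw treatment from a subject using, say, 121% of the dose; stopping can be left to the existing safety rules.

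The cost is rewording. The unblinded Investigator already holds the tube weights and diaries. A subject flagged at week 4 keeps at most 12 − 4 = 8 weekly visits and four follow-up visits, all already scheduled. The downside is that some poorly compliant subjects stay in the FAS, which may slightly dilute the effect. The person scoring the rule also knows gel from no gel, so it must leave no discretion.

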6.5 CONCOMITANT THERAPY

Any medication regularly used by the Subject including anti-diabetic medications as prescribed by the physician and approved by the Investigator will be permitted to be used.

If Investigator suspects infection at any wound site of the Subject, oral and/or parenteral antibiotics (except topical) and standard of wound care will be permissible to prevent the wound from leading to osteomyelitis. It will be at the Investigator's discretion to decide if it is necessary to defer the Study treatment to the Subject during the antibiotic treatment to control the wound infection. In case the non-Study ulcer is seen with infection, it will be treated with oral or parenteral antibiotics. The local antimicrobial therapy, if required will be permitted to the non-Study ulcer.

The concomitant medication administered must also be recorded in the CRF with generic name and/or trade name of the medication, dose, start and end dates of treatment.

6.5.1 RESCUE MEDICINE

Not applicable

7 STUDY INTERVENTION DISCONTINUATION AND PARTICIPANT DISCONTINUATION/WITHDRAWAL

7.1 DISCONTINUATION OF STUDY INTERVENTION

The subjects that report Osteomyelitis, cellulitis or SAE/AE where study intervention cannot be given, should be discontinued. For all discontinued Subjects, maximum possible and relevant Study information shall be gathered and be described in the source. This information can be gathered at Site visit or telephonically. If the discontinuation happens during the Treatment /Follow up Phase, the last visit prior to discontinuation will be treated as EOT/EOS visit and corresponding CRF will be completed by the Investigator.

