^j Subject Education and training on Diabetes management and use of off-loading device will be done as and when required

^k The AE reporting will begin from the application of the first dose of the IP from the Baseline Visit

^l Debridement of ulcer as and when necessary during site visit

^m Nutritional information should be provided to Subject as and when necessary

ⁿ Photographs of both the legs will be taken from various angles to ensure that there are no more than three ulcers on both the legs

^o In case the ulcer/wound closes within 12-weeks of Treatment Phase, the Subject will immediately enter the 12-weeks of Follow-Up Phase. In case of the Subject, whose Target Ulcer reopens during 12-weeks of Treatment Phase (within 84 days from Baseline) which is prior to the confirmation of Target Ulcer closure, the Subject would be given the treatment to complete 12-week of Treatment Phase

^p During Follow-Up Phase, if the Target Ulcer has reopened after confirmation of its closure, the Subject will still be continued with the Follow-up assessment.

^q This window period is from the Screening Visit

^r EOT is at week 12 visit or any visit on which first observation of Target Ulcer closure has happened or treatment is Stopped

^s EOS is at week 24 visit or any visit on which the Subject exits the Study

^t Window period of ±3 days will be allowed for each Treatment visit as well as FU1 and FU2 visits and window period of ±5 will be allowed for FU3 and FU4

Note: *Dispensing of Wound dressing material will be provided as long as required

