by the Study Nurse. Unless recommended by the Investigator otherwise, SoC during the Follow-Up Phase will be self-administered by the Subject.

Visit Schedule of the Subjects: Subjects in the Study will visit investigational site once a week during the 12-week Treatment Phase for wound measurement and for completing Study related assessments and procedures. In the Follow-Up (FU) Phase, the Subjects will visit investigational site at week 14, 16, 20 and 24.

Rules for Subject progression in the Study

The Subject progression in the Study will happen as per rules given in Table 1

Table 1 Subject progression as per condition of Target Ulcer

Sr. No.	Target Ulcer Closure within Treatment Phase	Reopened in Closure Confirmation period?	Action to be taken in the Study
1	Not closed	Not applicable	Proceed to Follow-Up Phase
2	Closed	No	Continue the Follow-Up Phase
		Yes	If reopened within 12-weeks from Baseline visit, continue treatment till EOT or Target Ulcer Closure, whichever is earlier and then proceed to Follow-Up Phase. If reopened after 12-weeks from Baseline visit, continue the Follow-Up Phase

The nomenclature used of various Study visits will be as follows:

Screening Visit: V1 or Day -10 to -7 (minus ten to minus seven) or Week -1 (minus one)

Treatment Visits:

V2 or Day 0 or Week 0 (also referred to as Baseline visit)

V3 or Day 7 or Week 1

V4 or Day 14 or Week 2

V5 or Day 21 or Week 3

V6 or Day 28 or Week 4

V7 or Day 35 or Week 5

V8 or Day 42 or Week 6

V9 or Day 49 or Week 7

V10 or Day 56 or Week 8

V11 or Day 63 or Week 9

V12 or Day 70 or Week 10

V13 or Day 77 or Week 11

V14 or Day 84 or Week 12 or End of Treatment (EOT)

Follow-Up (FU) Visits:

FU1 or V15 or Day 98 or Week 14 (also referred to as Closure Verification visit)

FU2 or V16 or Day 112 or Week 16 (also referred to as Closure Confirmation visit)

FU3 or V17 or Day 140 or Week 20

FU4 or V18 or Day 168 or Week 24 or End of Study (EOS)

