4.3 JUSTIFICATION FOR DOSE

Phase 1/2 clinical study of Galnobax® established that Galnobax® is safe for long term use (tested for 12-weeks) in both 14% and 20% concentrations. The efficacy analysis showed that Galnobax® treatment has advantage in terms of area and volume reduction over Placebo. The advantage of Galnobax® 14% is even more pronounced in hard to heal wounds. Considering this fact, this study has been planned to investigate Galnobax® 14% in a phase 3 trial to establish safety and efficacy in a larger number of Subjects for statistical significance.

Each eligible Study Subject will be assigned to one of the three treatment groups as described in Table 2 and will receive the next available consecutive randomization number.

Table 2 Dosing schedule

Gr. No.	Study group	Treatment frequency
1	Standard of Care + Galnobax® gel	Twice daily
2	Standard of Care	Twice daily
3	Standard of Care + Vehicle gel	Twice daily

Dose Modification for Study Drug

If any adverse reaction potentially related to Study drug is observed in terms of hypersensitivity or local allergic reaction at or around the Target Ulcer site, Investigator may decide to discontinue the

study drug administration to the Subject or adjust the frequency per the requirement for a limited period.

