Treatment Visits V3 to V14 (Week 1 to Week 12, Day 7 to Day 84 [Window period ± 3 days for each scheduled visit])

The Subjects assigned to Galnobax® plus SoC, Vehicle plus SoC or only SoC Group will receive the treatment twice daily from Study Nurse for up to 12-weeks or until complete closure of Target Ulcer, whichever is earlier.

All Subjects will visit the Study site once every week as given in Study calendar. Assessment will be done at various Treatment visits as follows:

- Urine pregnancy test will be performed (as applicable) after every 4 weeks till V14 or EOT, whichever is earlier
- Vital signs (blood pressure, pulse rate, respiratory rate, and temperature)
- Systematic physical examination and body weight after every 4 weeks till V14 or EOT, whichever is earlier
- Laboratory tests (hematology tests and biochemistry) after every 4 weeks till V14 or EOT, whichever is earlier
- HbA1c test at V14 or EOT, whichever is earlier

- Measurement of random blood glucose. If abnormality is observed, the Investigator may recommend pre- and post-prandial blood glucose measurement and modify dose or medication for adequate blood sugar control
- ECG or 2 D echocardiography (2D-ECHO only if ECG is not conclusive) after every 4 weeks till V14 or EOT, whichever is earlier
- X-ray of the foot under the Study will be taken at the Investigator's discretion for ruling out osteomyelitis. Other methods such as bone scan, leukocyte scan or MRI as needed may be used by the Investigator, for confirming the osteomyelitis depending on the Target Ulcer status
- Detail Foot Examination to assess vascular, neurological, dermatological and musculoskeletal signs and symptoms of the foot(s) with Target Ulcer after every 4 weeks till V14 or EOT, whichever is earlier
- Grading and staging of Target Ulcer as per Texas system of wound classification (See *Attachment 1*)
- Local examination and infection status of Target Ulcer for presence of edema, warmth, erythema, pain, scaling, pus, exudates, cellulitis, callus, maceration or swelling and any signs of infection
- Assessment of Target Ulcer characteristics in terms of wound edge, color, drainage amount and type, peri-wound conditions and color and percent wound bed covered by granulation tissue, fibrin slough, and necrotic tissue
- Surgical or Sharp debridement of Target Ulcer, if required along with documentation of type of debridement (e.g. callus removal, sharp or surgical), reason for debridement
- Target Ulcer measurement

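### Section 7.1 leaves open whether a Subject who permanently stops the gel for an adverse event stays in the Study, and nothing requires weekly blinded closure assessment afterwards, so an early stop with an open ulcer can leave the FAS

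*Combined protocol and SAP*

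**What the plan says.** Section 7.1 is headed as discontinuation of study intervention. Its operative sentence reads "The subjects that report Osteomyelitis, cellulitis or SAE/AE where study intervention cannot be given, should be discontinued". For a stop in the Treatment or Follow-Up Phase it adds that "the last visit prior to discontinuation will be treated as EOT/EOS visit". On data after the stop it asks for whatever relevant information can be had, and "This information can be gathered at Site visit or telephonically".

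Other text that bears on the point:

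- **Schedule of Activities, footnote r.** EOT is the week 12 visit or "any visit on which first observation of Target Ulcer closure has happened or treatment is Stopped".
- **Section 4.3, dose modification.** "If any adverse reaction potentially related to Study drug is observed in terms of hypersensitivity or local allergic reaction" at or around the Target Ulcer, the Investigator may stop the drug or change its frequency for a limited period. Nothing is said about assessments afterwards.
- **Section 4.3, Table 2.** Group 1 treatment is "Standard of Care + Galnobax® gel"; Group 2 is SoC alone.
- **Visit schedule.** Section 4.1: "Subjects in the Study will visit investigational site once a week during the 12-week Treatment Phase for wound measurement". Section 8, under Treatment Visits V3 to V14: "All Subjects will visit the Study site once every week as given in Study calendar".
- **Section 8, Follow-up Visit.** Entry to Follow-Up is on first closure or on completing 12 weeks. FU1 to FU4 fall 2, 4, 8 and 12 weeks after EOT.
- **Section 7.2.** Item 11 makes osteomyelitis or cellulitis on the target foot a reason to leave the Study. After withdrawal or discontinuation, only adverse-event recording and follow-up are requested.
- **Sections 9.3, 9.4.1 and 9.4.2.** The FAS needs six weekly closure assessments, or closure before six weeks. Efficacy is analysed in the FAS and PP sets only; the ITT set is for safety.

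**The concern.** Two sites could follow 7.1 in good faith and act differently. One stops the gel, continues SoC and sees the Subject weekly. The other treats the last visit as EOT or EOS and collects what it can, possibly by telephone.

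Under the second practice, a Subject who stops before six weekly assessments with an open ulcer is outside the FAS. If participation also ends, the Subject has not completed the Study and is outside the PP set too. No planned efficacy analysis then includes that Subject, and Section 9.4.7 leaves missing-data handling to the SAP. Weekly closure assessments that were never made cannot be recovered by a later analysis plan.

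The loss matters more because one of its causes is tied to arm. Group 2 receives no gel, so a stop for a gel reaction can happen only in Group 1 of the efficacy comparison. Section 8.2.3.3 lists hypersensitivity, irritation and ulcer inflammation among the expected events.

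**Working it through.** **Step 1. Which stops are affected.** Target-foot osteomyelitis or cellulitis is Study exit under 7.2 item 11. Section 6.5 allows treatment to be deferred during antibiotic treatment, which is temporary. What remains is a permanent gel stop for another AE or SAE.

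**Step 2. What happens after such a stop.**

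| Text | Only the gel stops | Treatment Phase or participation ends |
|---|---|---|
| 7.1 heading | Refers to intervention | |
| 7.1 last sentence | | Last visit becomes EOT/EOS, as in 7.2 for withdrawal |
| Footnote r | | Visit at which treatment stops is EOT |
| Table 2 | SoC is part of treatment and could go on | |
| 4.1 and Section 8, weekly visits | Apply to all Subjects | Written for the Treatment Phase |
| Section 8, Follow-Up entry | Gel stop not listed | Gel stop not listed |
| FU1 to FU4 | | Not weekly |

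Neither column is ruled out. No text requires weekly blinded closure assessment after the stop.

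**Step 3. When the FAS is affected.** Weekly visits start at V3 (week 1), so the sixth is V8 (week 6, Day 42), not counting Baseline. A Subject whose weekly assessments end before V8 with an open ulcer fails the FAS rule. One who stops later stays in the FAS.

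**Step 4. The plan's own figures.** Section 9.2 uses 39% against 60%, two-sided 0.05 and 90% power. The pooled two-proportion formula without continuity correction gives 118 per group against the stated 120. Then 240 / (1 - 0.20) = 300 randomized in Groups 1 and 2, or 150 each. The sample size is not in dispute; it supplies the 150, 39% and 60% used below.

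**Step 5. Size, by illustration.** The documents give no stop rate, so k is assumed. Let k of 150 Group 1 Subjects stop, let the other 150 - k close at 60%, let p be the closure rate the stopped Subjects would have had, and assume no other drop-outs.

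- Rate in all 150 = [0.60 × (150 - k) + k × p] / 150.
- All stops early: FAS rate = 60.0%, so the shift is k × (0.60 - p) / 150. Per stop this is 0.21/150 = 0.14 points at p = 39%, or 0.60/150 = 0.4 points at p = 0.
- All stops late, with exit and counted as not closed: FAS rate = 0.60 × (150 - k) / 150, so the shift is -k × p / 150. Per stop this is -0.39/150 = -0.26 points at p = 39%, or 0 at p = 0.

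| k | All early, p = 39% | All early, p = 0 | All late, p = 39% | All late, p = 0 |
|---|---|---|---|---|
| 5 | +0.7 | +2.0 | -1.3 | 0 |
| 10 | +1.4 | +4.0 | -2.6 | 0 |
| 15 | +2.1 | +6.0 | -3.9 | 0 |

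**Step 6. Direction.** With e of the k stops early, FAS rate = 0.60 × (150 - k) / (150 - e). At p = 39% this equals the rate in all 150 when e is 3.3 of 5, 6.7 of 10 or 10.1 of 15. The Group 1 rate is raised only if more than about two thirds of stops are early. Exits under 7.2 items 9 to 11 also remove open ulcers, in both groups.

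**The case against.** The plan is not blind to the distinction. Sections 7.1 and 7.2 have separate headings, 4.3 speaks of stopping the drug rather than leaving the Study, and the weekly-visit sentences cover all Subjects. That stands: a reader might infer that every gel stop is Study exit, and the documents do not say so. They leave it open.

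Section 4.3 offers reduced frequency as an alternative to stopping, and the single drug-related event on 14% in Phase 1/2 (Section 2.3.1) was mild and reversible. Permanent stops may be rare. That stands too, and that event is not scaled up here.

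Section 7.1 refers to study intervention, and Section 8.2.1 counts SoC alone as an intervention, so an adverse-event stop can occur in Group 2. Agreed: only stops for gel reactions are confined to Group 1.

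A reader might also infer that weeks off the gel are 0% compliant, so that 6.4 and 7.2 item 6 force exit. Section 6.4 ties compliance to the application weight prescribed at each visit, and after an authorised stop nothing is prescribed. Whether such weeks count is unclear. Exit would also need the blinded Investigator's opinion. More than three such weeks means four, so for a stop at week 2 the count is reached only at week 6; this route could affect FAS membership only for stops before about week 2.

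Finally, 7.1 could mean EOT for a Treatment Phase stop and EOS for a Follow-Up stop. If the Subject then entered Follow-Up, closure would still be observed at FU1 to FU4. But the entry sentence does not list a gel stop, and those visits are not weekly, so they do not clearly satisfy the FAS rule.

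**Conclusion.** The gap is real and limited. It concerns a permanent gel stop for an AE or SAE other than target-foot osteomyelitis or cellulitis. For such a stop, continued participation is undefined, footnote r points to EOT, and weekly blinded assessment is not required. If weekly assessment ends before V8 with an open ulcer, the Subject drops out of the FAS.

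The size rests on assumed stop counts, 150 in Group 1, 60% closure among the rest and no other losses. Each early stop adds about 0.14 to 0.4 points to the Group 1 rate, against a planned difference of 21 points. The 6.0-point figure needs 15 stops, all early, none of which would have closed.

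A reader might infer that the trial is biased towards Galnobax or that its Type I error is inflated by a known amount. The documents support neither, because the stop rate, its timing and the net direction are unknown. The case for acting is that primary-outcome assessments can be lost partly for an arm-linked reason, and that preventing this costs little. It is a cheap improvement that should be made.

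**What to change.** Reword 7.1 so that, when an AE or SAE prevents use of the study gel, only the gel (if any) is stopped. This includes osteomyelitis or cellulitis elsewhere than the target foot. The Subject stays in the Study on SoC and, where medically able and consenting, attends the remaining weekly visits to V14 or first closure for blinded Target Ulcer assessment. FU1 to FU4 are timed from that visit. Target-foot osteomyelitis or cellulitis stays under 7.2 item 11.

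Conforming changes:

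1. Footnote r: a gel stop alone is not EOT.
2. Last sentence of 7.1: limit it to a stop of all assigned treatment, and remove the Follow-Up Phase and EOS from it.
3. Section 8: add these Subjects to the sentence on entry to Follow-Up.
4. Sections 6.4 and 7.2 item 6: weeks after an authorised gel stop are not counted as non-compliant.

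The words if any let the blinded Investigator give the instruction without knowing the arm; the unblinded Investigator and Study Nurse carry it out. The FAS rule itself is unchanged.

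The cost is a protocol amendment with EC approval before use, at about 40 sites, and continued visits and nurse dressings for the Subjects affected, probably few. The weekly visits are already in the schedule.
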